3.5. Safety Endpoints

3.5.1. Local Reactions

Local reaction data are solicited AEs. The local reactions assessed and reported in the e-diary are redness, swelling, and pain at the injection site of study intervention, from Day 1 through Day 7 after each vaccination, where Day 1 is the day of vaccination. This section describes derivations with details for the assessment of local reactions: presence, severity level, duration, and onset day.

Presence

For each local reaction, the derivation of whether or not the specific reaction occurred on each day and “any day (Days 1-7, where Day 1 is the day of vaccination)” will be made. The variable will be calculated for each vaccination as well as overall reactions for any vaccination. The derivation of this variable is given in Table 5.

Table 5. Derived Variables for Local Reactions

Variable	Yes (1) ^a	No (0) ^b	Missing (.)
Each day (Days 1-7)	Participant/parent/legal guardian reports the reaction as “mild,” “moderate,” or “severe” on each individual day.	Participant/parent/legal guardian reports the reaction as “none” on the individual day.	Participant did not report on the reaction on the individual day.

Table 5. Derived Variables for Local Reactions

Variable	Yes (1) ^a	No (0) ^b	Missing (.)
Any day (Days 1-7)	Participant/parent/legal guardian reports the reaction as “mild,” “moderate,” or “severe” on any day (Days 1-7).	Participant/parent legal guardian reports the reaction as “none” on all 7 days or as a combination of “none” and missing on all 7 days.	Participant did not report on the reaction on any of the 7 days.

a. For redness and swelling, “mild,” “moderate, and “severe” categories are based on the caliper size reported from the e-diary and defined in Table 6.

b. For redness and swelling, “none” means 0 to 4 caliper units reported in the e-diary.

Severity and Maximum Severity

A caliper (measuring device) is used to measure the redness or swelling of the injection site area. Caliper units (range: 1-21+) are converted to centimeters according to 1 caliper unit = 0.5 centimeters and then categorized as none, mild, moderate, or severe based on the grading scale of local reactions in Table 6. The caliper will be used to measure and to report the largest diameter of a redness or swelling at the injection site. In the event that a caliper measurement is between 2 values, the higher value should be reported. Pain at the injection site will be assessed by the participant/parent(s)/legal guardian(s) according to the grading scale in Table 7. The measurements will then be recorded in the e-diary.

Table 6. Grading of Redness and Swelling

None	0 to 2.0 cm (0 to 4 caliper units)
Mild	>2.0 to 5.0 cm (5 to 10 caliper units)
Moderate	>5.0 to 10.0 cm (11 to 20 caliper units)
Severe	>10.0 cm (>20 caliper units)

Table 7. Grading of Pain at Injection Site

Mild	Does not interfere with activity
Moderate	Interferes with activity
Severe	Prevents daily activity

The maximum severity (highest grading) of each local reaction within 7 days after vaccination will be derived for each vaccination as well as for any vaccination. The maximum severity will be derived as follows:

- = •, if values are missing for all days (Days 1 to 7);
- = 0, if the participant's parent(s)/legal guardian(s) reports all reactions as "none" or a combination of missing and "none" for all days (Days 1 to 7);
- = *highest grade* (maximum severity) within 7 days after vaccination, if the answer is not "none" for at least 1 day.

Duration

For participants experiencing any local reactions (or those with derived reaction presence in [Table 5](#)), the maximum duration (last day of reaction - first day of reaction + 1) will be derived for the study vaccination. Resolution of the event is the last day on which the event is recorded in the e-diary or the date the event ends if it is unresolved during the participant diary-recording period (end date collected on the CRF), unless chronicity is established. If there is no known end date, the duration will be considered unknown and set to missing.

For reactions that continue into the next vaccination visit, the duration will be calculated in a segmented fashion. The reaction end date will be set to the day prior to the next vaccination and will have a new start date as the day of next vaccination. The duration will be calculated separately from the new start date to the date of resolution. Participants with reactions spanning multiple vaccination visits will be included in a footnote.

Participants with no reported reaction have no data for duration.

Onset Day

The onset day of each local reaction will be derived. The onset day is defined as the first day of reporting the reaction with any severity after vaccination.

In summary, the following variables will be derived for local reactions:

- Each local reaction on each day (Days 1 to 7) after each vaccination.
- Each local reaction on any day (Days 1 to 7) after each vaccination and any vaccination.
- Any local reaction on any day (Days 1 to 7) after each vaccination and after any vaccination.
- Maximum severity of each local reaction on any day (Days 1 to 7) after each vaccination and after any vaccination.

- Maximum duration of each local reaction after each vaccination.
- Onset day of each local reaction after each vaccination.

3.5.2. Systemic Events

The systemic events assessed and recorded in the e-diary are fever, vomiting, diarrhea, headache, fatigue, chills, muscle pain other than muscle pain at the injection site, and joint pain, from Day 1 through Day 7, where Day 1 is the day of vaccination. The systemic events will be assessed by participants or parents/legal guardians as mild, moderate, or severe according to the grading scale in Table 8.

Table 8. Grading of Systemic Events Other Than Fever

	Grade 1 (Mild)	Grade 2 (Moderate)	Grade 3 (Severe)
Vomiting	1 to 2 times in 24 hours	>2 times in 24 hours	Requires IV hydration
Diarrhea	2 to 3 loose stools in 24 hours	4 to 5 loose stools in 24 hours	6 or more loose stools in 24 hours
Headache	Does not interfere with activity	Some interference with activity	Prevents daily routine activity
Fatigue	Does not interfere with activity	Some interference with activity	Prevents daily routine activity
Chills	Does not interfere with activity	Some interference with activity	Prevents daily routine activity
Muscle pain (other than muscle pain at the injection site)	Does not interfere with activity	Some interference with activity	Prevents daily routine activity
Joint pain	Does not interfere with activity	Some interference with activity	Prevents daily routine activity

Abbreviation: IV = intravenous.

Maximum oral temperature range over the period from Day 1 through Day 7 after each vaccination will be mapped into the ranges described in Table 9 for summary of maximum temperature. The highest temperature for each day will be recorded in the e-diary. Fever is defined as temperature of $\geq 38.0^{\circ}\text{C}$ (100.4°F).

Table 9. Severity Scale for Fever

Temperature 38.0°C to 38.4°C (100.4°F to 101.1°F)
Temperature $>38.4^{\circ}\text{C}$ to 38.9°C (101.2°F to 102.0°F)
Temperature $>38.9^{\circ}\text{C}$ to 40.0°C (102.1°F to 104.0°F)
Temperature $>40.0^{\circ}\text{C}$ ($>104.0^{\circ}\text{F}$)

For each systemic event, the following variables will be available, similar to local reactions:

1. Each systemic event on each day (Days 1 to 7) after each vaccination.
2. Each systemic event on any day (Days 1 to 7) after each vaccination and after any vaccination.
3. Any systemic event on any day (Days 1 to 7) after each vaccination and after any vaccination.
4. Maximum severity of each systemic event on any day (Days 1 to 7) after each vaccination and after any vaccination.
5. Maximum duration of each systemic event after each vaccination.
6. Onset day of each local reaction after each vaccination.

The derivation of severity, maximum severity, duration, and onset day for systemic events is similar to the derivation of the variables for local reactions ([Section 3.5.1](#)).

3.5.3. Use of Antipyretic Medication

The use of antipyretic medication (yes/no) will be recorded in the e-diary for 7 days (Day 1 to Day 7) after each vaccination.

The following variables will be derived:

1. Use of antipyretic medication on each day (Days 1 to 7) after each vaccination.
2. Use of antipyretic medication on any day (Days 1 to 7) after each vaccination and after any vaccination.
3. Maximum duration of use of antipyretic medication after each vaccination.

Three analysis intervals will be applied to reactogenicity data (Table 10).

Table 10. Analysis Intervals for Reactogenicity Data

No.	Analysis Interval	Analysis Population	Interval Start Date (Inclusive)	Interval Stop Date (Inclusive)
1	Vaccination 1	Vaccination 1 safety	Vax 1 date	Vax 1 date + 6 days (or until date of resolution)
2	Vaccination 2	Vaccination 2 safety	Vax 2 date	Vax 2 date + 6 days (or until date of resolution)
3	Any vaccination	Safety	Vax 1 or Vax 2 date	Vax 1 or Vax 2 date + 6 days (or until date of resolution)

3.5.4. Adverse Events

The relationship between (S)AEs and the study intervention will be characterized as related or not related as determined by investigators and as described in the protocol. The severity of AEs will be characterized as mild, moderate, and severe. Immediate AEs will be assessed within the first 30 minutes after each vaccination.

An NDCMC is defined as a disease or medical condition not previously identified that is expected to be persistent or otherwise long-lasting in its effects. An MAE is defined as a nonserious AE that results in an evaluation at a medical facility, and participants who missed days of school or work because of an AE will be captured via the AE checklist ([Section 2.3](#)).

(S)AEs will be actively collected for each participant beginning from the time the participant or parent(s)/legal guardian provides informed consent, which is obtained before the participant's participation in the study (ie, before undergoing any study-related procedure and/or receiving study intervention), through and including Visit 4. At Month 12 (Visit 5, telephone contact), the parent(s)/legal guardian or participant will be contacted by telephone to inquire about AEs, SAEs, MAEs, NDCMCs, and days missing from school or work because of AEs that resulted in evaluation at a medical facility since Visit 4.

Significant medical occurrences that begin before consent will be recorded on the Medical History/Current Medical Conditions section of the CRF, not the AE section. All events collected on the CRF will be categorized according to the current version of MedDRA (at the time of reporting).

There will be 6 analysis intervals for the AE data collected via the CRF (Table 11). The analysis populations used for these intervals are described in detail in [Section 4](#).

Table 11. Analysis Intervals for AEs, SAEs, MAEs, NDCMCs, and Days Missing School or Work Because of AEs

No.	Analysis Interval	Analysis Population	Interval Start Date (Inclusive)	Interval Stop Date (Inclusive)	Safety Data
1	Within 30 days after Vaccination 1	Vaccination 1 safety	Vax 1 date	Vax 1 date + 30 days	AEs, SAEs, MAEs
2	Within 30 days after Vaccination 2	Vaccination 2 safety	Vax 2 date	Vax 2 date + 30 days	AEs, SAEs, MAEs
3	Within 30 days after any vaccination	Safety	Vax 1 date or Vax 2 date	Vax 1 date + 30 days or Vax 2 date + 30 days	AEs, SAEs, MAEs
4	During the vaccination phase (from Vaccination 1 through 1 month after Vaccination 2)	Safety	Visit 1 date	Visit 4 date	AEs, SAEs, MAEs, NDCMCs, days missing from school or work because of AEs

Table 11. Analysis Intervals for AEs, SAEs, MAEs, NDCMCs, and Days Missing School or Work Because of AEs

No.	Analysis Interval	Analysis Population	Interval Start Date (Inclusive)	Interval Stop Date (Inclusive)	Safety Data
5	During the follow-up phase (from 1 month after Vaccination 2 through 6 months after Vaccination 2)	Follow-up safety	Visit 4 date + 1	Visit 5 date	SAEs, MAEs, NDCMCs
6	From Vaccination 1 through 6 months after Vaccination 2	Safety	Visit 1 date	Visit 5 date	SAEs, MAEs, NDCMCs

Abbreviations: MAE = medically attended adverse event; NDCMC = newly diagnosed chronic medical condition.

Two analysis intervals will be applied to immediate AEs (Table 12).

Table 12. Analysis Intervals for Immediate AEs

No.	Analysis Interval	Analysis Population	Interval Start Date/Time (Inclusive)	Interval Stop Date/Time (Inclusive)
1	Dose 1	Vaccination 1 safety	Vax 1 time	Vax 1 time + 30 minutes
2	Dose 2	Vaccination 2 safety	Vax 2 time	Vax 2 time + 30 minutes

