## 8.2. Safety Assessments

Planned time points for all safety assessments are provided in the [SoA](#). Unscheduled clinical laboratory measurements may be obtained at any time during the study to assess any perceived safety issues.

Any participant who receives at least 1 dose of study intervention will be included in the evaluation for safety. The following safety parameters will be assessed as described in [Section 8.11](#) and in the [SoA](#):

- Physical examination.
- Reactogenicity: local reactions and systemic events, including fever.
- Use of antipyretic medication.
- Unsolicited AEs and SAEs.

A medical history will be obtained and a physical examination will be performed on all participants at Visit 1 to establish a baseline. When taking the medical history and performing the physical examination, particular care must be taken to note any neuroinflammatory and autoimmune conditions, such as transverse myelitis, uveitis, optic neuritis, and multiple sclerosis. Significant medical history and observations from the physical examination will be documented on the CRF.

The safety parameters include reactogenicity, ie, both local reactions and systemic events that occur in the 7 days (Days 1 through 7, where Day 1 is the day of vaccination) after study intervention administration. These prompted e-diary events are:

- Local reactions at the site of study intervention administration (redness, swelling, and pain at the injection site).
- Systemic events (fever, vomiting, diarrhea, headache, fatigue, chills, muscle pain other than muscle pain at the injection site, and joint pain).

Local reactions, systemic events, and use of antipyretic medication will be collected using an e-diary. For events that resolve after Day 7, the end date will be collected in the CRF. If a participant does not complete the e-diary for 7 days, end dates of local reactions, systemic events, or antipyretic medication use that was ongoing on the last day the e-diary was completed by the participant will be collected on the CRF.

Immediate AEs, defined as AEs occurring within the first 30 minutes after study intervention administration, will be assessed and documented on the AE CRF. The time of onset will be recorded for any AEs that occur on the same day as study intervention administration.

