### **8.3.1.2. Recording Nonserious AEs and SAEs on the CRF**

All nonserious AEs and SAEs occurring in a participant during the active collection period as described in [Section 8.3.1](#) are recorded on the CRF. AEs and SAEs that begin after obtaining informed consent but before the start of administration of study intervention will be recorded on the Medical History/Current Medical Conditions section of the CRF, not the AE section. AEs and SAEs that begin after the start of administration of study intervention are recorded on the AE section of the CRF.

The investigator is to record on the CRF all directly observed and all spontaneously reported AEs and SAEs reported by the participant.

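### SAP Table 11 dates AEs by calendar day, so an event that began before the second injection on the Visit 3 day is tabulated as following Vaccination 2

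*SAP*

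**What the plan says.** **Interval limits.** In SAP 3.5.4, the start column of Table 11 is headed "Interval Start Date (Inclusive"). Intervals 1 and 2 open on the Vaccination 1 and Vaccination 2 dates and close 30 days later. Interval 3 is either of these windows. Intervals 4 and 6 open on the Visit 1 date. Table 12, for immediate AEs only, has a start column headed "Interval Start Date/Time (Inclusive") and runs from the vaccination time to 30 minutes afterwards.

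**Times collected.** Protocol 8.2 states: "The time of onset will be recorded for any AEs that occur on the same day as study intervention administration". Protocol 8.11.3 repeats this for Visit 3 and also has the time of injection entered on the CRF.

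**Where events are recorded.** Protocol 8.3.1.2 deals expressly with the gap between consent and the first injection. Its wording for events in that gap is "begin after obtaining informed consent but before the start of administration of study intervention will be recorded on the Medical History/Current Medical Conditions section". For everything later, the rule is: "AEs and SAEs that begin after the start of administration of study intervention are recorded on the AE section of the CRF". SAP 3.5.4 starts AE collection at consent and then says: "Significant medical occurrences that begin before consent will be recorded on the Medical History/Current Medical Conditions section of the CRF, not the AE section".

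**The concern.** Intervals 1 to 3 are labelled as periods after a vaccination, but the rule that fills them cannot tell the hours before the injection from the hours after it. At Visit 3 the participant has already had dose 1, so a new event that morning is on the AE page and goes into the post-Vaccination 2 tables. These intervals feed primary safety estimands (AEs, SAEs and MAEs within 30 days of each and of any vaccination) in a study of at most 50 participants. In a descriptive report, one such event can turn no cases after dose 2 into one case.

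The consent sentence in the SAP adds a second uncertainty. If it were taken as the operative rule, an event between consent and the first injection would belong on the AE page, and the same date rule would then count it after Vaccination 1.

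**Working it through.** The plan gives no figure for this point, so there is none to reproduce. The check is a comparison of the rules, followed by the scale.

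**1. Visit 3 (dose 2).** Take an injection at 10:00 and an AE with onset at 08:00 the same day (illustrative times).
- CRF location under protocol 8.3.1.2: the AE page, because first administration has already taken place.
- Table 11 rule, onset date ≥ vaccination date: true, so it is counted.
- Time rule as in Table 12, onset time ≥ injection time: 08:00 ≥ 10:00 is false, so it is not counted.
- Interval 2 therefore counts an event that preceded the dose.
- Interval 3 does too. Visit 3 falls 173 to 194 days after Visit 1, so the event lies well outside 30 days of Vaccination 1 and can enter only through the Vaccination 2 window.
- Intervals 4 and 6 cover time since Vaccination 1. The event belongs in interval 4, and in interval 6 if it is an SAE, MAE or NDCMC.

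**2. Visit 1 (dose 1), event after consent and before injection.**

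| Rule followed | CRF section | Table 11 result |
|---|---|---|
| Protocol 8.3.1.2 | Medical History | In no AE interval |
| SAP 3.5.4, read by implication | AE | Intervals 1, 3 and 4, and 6 if an SAE, MAE or NDCMC, when dated on the vaccination day |

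The SAP sentence does not name the period between consent and dosing. The second row is an inference from its consent cut-off and from AE collection starting at consent.

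**3. Is there a time rule elsewhere?** The SAP contains no definition of a post-dose or treatment-emergent AE. The sponsor safety rules it cites deal with missing AE dates. Its Introduction says that programming rules are kept in a separate document, which is not available here.

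**4. Scale.** One participant at N=50: 1/50 = 2.0 percentage points. Exact (Clopper-Pearson) 95% CIs:
- 0/50 = 0% (0 to 7.1%) becomes 1/50 = 2% (0.05 to 10.6%).
- 5/50 = 10% (3.3 to 21.8%) becomes 6/50 = 12% (4.5 to 24.3%).

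Interval 2 uses those who received dose 2, so its denominator may be smaller. If 45 were dosed (an assumption), the step is 1/45 = 2.2 points; if 40, 1/40 = 2.5 points.

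**The case against.** The case against is strong on dose 1 and partial on dose 2.

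- **Dose 1.** The SAP and protocol sentences can both be true: one concerns events before consent, the other also covers events between consent and dosing. Sites work to the protocol, and Table 11 applies to AE data collected on the CRF. With the CRF completed as protocol 8.3.1.2 directs, events before dose 1 are not on the AE page and cannot enter any interval. This stands.
- **Blood-draw events.** Fainting or bruising at a pre-dose blood draw is an obvious example, but the only pre-dose draw is at Visit 1, where the protocol rule deals with it. Visit 3 has no blood draw. This stands.
- **Few events at Visit 3.** Protocol 5.5.1 delays vaccination for febrile or other acute illness in the previous 48 hours, so many same-day illnesses would move the dose to another date. That reduces the number of affected events but does not remove them: an AE that is not an acute illness, such as a minor injury, can still begin that morning.
- **Controls.** SAP 2.2.1 reports the B1971057 controls over the same intervals, from existing analysis data sets. The documents do not show that onset times are in those data sets. A time rule applied to one group only would make the two sets of tables unlike. This stands and shapes the fix.
- **Unseen rules.** The separate programming rules may already contain a time condition. If so, the SAP need only state it.

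**Conclusion.** The Visit 3 point holds. As written, Table 11 attributes to Vaccination 2 an AE that began earlier the same day, in intervals 2 and 3, although the data needed to avoid this are collected. Immediate AEs are unaffected, and intervals 4 and 6 are right for such an event.

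For dose 1 there is only a wording difference by implication. It would matter only if the SAP sentence were followed over the protocol.

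A reader might infer that the two documents yield different AE counts from the same events, or that the vaccination-phase percentages are inflated by events before the first dose. The documents do not support either reading, because the protocol's recording rule keeps those events off the AE page. Nor do intervals 4 and 6 need a new start. Visit 1 is the Vaccination 1 visit, and if dosing is delayed, protocol 5.5.1 and 8.11.1 move or repeat the visit procedures on the vaccination day.

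The effect is probably small: 2 percentage points per participant at N=50. The number of such events is not given, so no expected bias can be calculated. The conclusion assumes that no time rule exists in the separate programming document.

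**What to change.** 1. Reword the SAP 3.5.4 sentence so that the Medical History cut-off is the start of first administration, as in protocol 8.3.1.2.
2. Add a note to Table 11: an AE with onset on a vaccination date counts as post-dose for that vaccination only if its onset time is at or after the injection time; if the onset time is missing, it counts as post-dose.
3. Apply the same condition to the B1971057 controls if their onset times are in the analysis data sets. If they are not, keep the date rule for both groups in the side-by-side tables, and identify same-day pre-injection events in a listing or footnote.

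The cost is two SAP wording changes, one programming condition, and a check of whether the control data sets hold onset times. No new data are needed from participants in this study, and the protocol does not change.

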3.5.5. Pregnancy Testing

A pregnancy test for all female participants will be conducted at Visits 1 and 3.

3.5.6. Laboratory Data

Laboratory assessments will not be collected for this study.

3.5.7. Medical Device Errors

Medical device incidents or malfunctions of the device that result in an incident will be detected, documented, and reported during all periods of the study in which the medical device is used. If a medical device error involves an AE, it will be summarized according to AE reporting conventions.

